**Table 1. Summary of post-enrollment assessments.**

Subjects:	All							Participating in Crossover *							All
Time Point Following:	Initial Treatment							Crossover Treatment							Initial
Time Point (Days):	0	1	7					0	1	7					
Time Point (Months):			1		2	3	4			1		2	3	4	12
Brief Pain Inventory (for Phantom Limb Pain)	•	•	•	•	•	•	•	•	•	•	•	•	•	•	•
Residual Limb Pain (NRS)	•	•	•	•	•	•	•	•	•	•	•	•	•	•	•
Patient Global Impression of Change Scale	•	•	•	•	•	•	•	•	•	•	•	•	•	•	•
Beck Depression Inventory	•							•							•
Non-Painful Phantom Sensations	•	•	•	•	•	•	•	•	•	•	•	•	•	•	•
Phantom Limb Pain	•	•	•	•	•	•	•	•	•	•	•	•	•	•	•
Residual Limb Pain	•	•	•	•	•	•	•	•	•	•	•	•	•	•	•

\* The second—or “crossover”—treatment intervention will occur between 4-6 months following the initial treatment

**Demographic and amputation history.** Subjects will have demographic data collected, including

age, sex, height, weight, educational level, employment status, marital status, current analgesic regimen (including adjuvants such as acupuncture), and U.S. military service (e.g., none, discharged, active). In addition, amputation-specific data will include date of initial amputation, date(s) of subsequent surgical procedures, amputation etiology, amputation level, other amputations (with dates/etiology/pain), and prosthesis use.

**Hypothesis 1:** Phantom limb pain **intensity** will be significantly decreased 4 months following one cryoneurolysis procedure (as measured by the Numeric Rating Scale within the Brief Pain Inventory).

**Pain intensity.** Current/present, worst, least, and average phantom pain will be assessed using a Numeric Rating Scale (NRS) as part of the Brief Pain Inventory (short form), with the “average” pain score designated as the primary endpoint. In addition, average and worst residual limb pain NRS will be recorded separately from the phantom pain scores. The NRS is a highly-sensitive measure of pain intensity with numbers ranging from 0 to 10, zero equivalent to no pain and 10 equivalent to the worst imaginable pain. The NRS has been demonstrated to be a valid and reliable measure in multiple pain states—including painful peripheral neuropathy specifically—and following analgesic interventions. In addition, NRS scores correlate well with other measures of pain intensity, and demonstrate high test-retest reliability in chronic nociceptive and neuropathic pain states. These NRS characteristics led to recent IMMPACT consensus recommendations for use of the 10-point NRS of pain intensity for chronic pain trials.

**Hypothesis 2a:** Perception of **well-being** will be significantly improved 4 months following one cryoneurolysis procedure (as measured with the Patient Global Impression of Change Scale).

**Health-related quality of life.** While single-item measures of pain level/relief are currently the most reliable and valid options to measure pain intensity, the multidimensional aspect of the pain experience has led consensus recommendations for use of “global” measures of improvement in chronic pain trials. The Patient Global Impression of Change Scale is one such measure allowing patient evaluation of integrated treatment effects. This measure is a 7-point ordinal scale requiring the subject to rate the current severity of their global situation as it relates to phantom limb pain (as defined by each individual) compared to their baseline. This scale has the words “very much worse” to the left by the number one, and “very much improved” to the right, adjacent to the number seven. The words “no change” are in the middle of the scale above the number four. The Patient Global Impression of Change Scale has been validated in over ten prospective trials, including studies specifically involving peripheral neuropathy.

**Hypothesis 2b:** Physical and emotional **functioning** will be significantly improved 4 months following one cryoneurolysis procedure (as measured with the Brief Pain Inventory).

It is well-recognized that, “pain is a complex, multidimensional, sensory, and emotional experience that is individually perceived and described in many different ways.” This observation has led to

consensus recommendations that “multiple core domains and related measures be considered in pain treatment trials,” that “tap into a wider experience of pain over time and its impact on functioning and quality of life.” Therefore, the proposed trial will include the Brief Pain Inventory, an instrument that includes—in addition to pain intensity scales—seven measures evaluating the pain’s interference with physical and emotional functioning, such as sleep, relations with others, and enjoyment of life. The Brief Pain Inventory has been used in countless clinical studies of chronic pain, and validated specifically in neuropathic pain states. This instrument is associated with minimal subject burden and is easily interpreted by patients of all ages and education levels. It has high test-retest reliability and correlates well with much longer questionnaires, including the McGill measures and EuroQol.

**Hypothesis 2c: Depression** will be significantly decreased 4 months following one cryoneurolysis procedure (as measured with the Beck Depression Inventory).

In addition, multiple investigations demonstrate that factors such as anxiety and depression are strong predictors of pain intensity. Therefore, the proposed study will evaluate additional psychosocial factors using the Beck Depression Inventory. This 21-item instrument measures characteristic symptoms and signs of depression, requires only a 5th grade comprehension level to adequately understand the questions, and demonstrates high internal consistency (0.73-0.92, mean of 0.86), reliability and validity. Each of the 21 factors is rated on a 0-3 scale, and then summed to produce the total score of 0-63. Mild, moderate, and severe depression is defined with scores of 10-18, 19-29, and 30-63, respectively. While this instrument requires less than 10 minutes to complete, on average, it will be administered only at the initial baseline and four months following each treatment intervention (initial and crossover) as well as Month 12 to minimize subject burden and fatigue.

**Additional pain-related data.** Frequency and average duration of non-painful phantom sensations, phantom limb pain, and residual limb pain will be assessed. In addition, supplemental analgesic use will be recorded, and other pain locations/severity will be evaluated using the NRS. Lastly, to investigate masking adequacy, subjects will be queried on Day 0 following the treatment procedure on which treatment they believe they received (active cryoneurolysis vs. sham/placebo).

**Data collection.** Subject demographic and cryoneurolysis administration data will be uploaded from each enrolling center *via* the Internet to a secure, password-protected, encrypted central server (RedCap, Cleveland Clinic, Cleveland, Ohio). The questionnaires for all subjects—regardless of enrolling center—will be administered by telephone from the University of California San Diego by research coordinators specifically trained in these instruments’ application, minimizing inter-rater discordance. Staff masked to treatment group assignment will perform all assessments. This web-based data-collection protocol has been used successfully by the investigators for numerous previously published multicenter clinical trials. Each data collection phone call will require approximately 15 minutes, with any time point including the Beck Depression Inventory requiring an additional 15 minutes.

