**6. SPECIFIC AIMS**

The ultimate objective of the proposed research is to determine if cryoanalgesia is an effective

treatment for intractable post-amputation phantom limb pain.

**Primary Specific Aim:** To test the influence of a cryoanalgesia treatment as compared to sham/placebo on the intensity of existing, intractable phantom limb pain resulting from an amputation.

**Hypothesis 1:** Phantom limb pain **intensity** will be significantly decreased 4 months following one cryoneurolysis procedure (as measured by the Numeric Rating Scale within the Brief Pain Inventory).

**Secondary Specific Aim:** To test the influence of a cryoanalgesia treatment as compared to sham/placebo on the quality of life for individuals with intractable phantom limb pain resulting from an amputation.

**Hypothesis 2a:** Perception of **well-being** will be significantly improved 4 months following one cryoneurolysis procedure (as measured with the Patient Global Impression of Change Scale).

**Hypothesis 2b:** Physical and emotional **functioning** will be significantly improved 4 months following one cryoneurolysis procedure (as measured with the Brief Pain Inventory).

**Hypothesis 2c:** **Depression** will be significantly decreased 4 months following one cryoneurolysis procedure (as measured with the Beck Depression Inventory).

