### **Secondary outcomes.**

**Aim 2a.** The randomized groups will be compared on the global measure of improvement (Patient Global Impression of Change Scale) at 4 months using the Mann-Whitney test. Proportional odds logistic regression will be used to adjust for any imbalanced baseline variables, as appropriate.

**Aim 2b.** The randomized groups will also be compared at 4 months on the seven measures of Brief Pain Inventory, which evaluate pain's interference with physical and emotional functioning. We will use a mixed effects multivariate model (random subject term, fixed treatment effect, unstructured correlation matrix) to first assess whether the treatment effect differs across the individual measures (i.e., treatment-measure interaction). In presence of an interaction, each measure will be evaluated univariably. Otherwise, an overall treatment effect will be estimated from the mixed effects model as the primary result for this aim.

**Aim 2c.** Analysis of covariance adjusting for baseline score will be used to assess the treatment effect of cryoneurolysis versus sham on depression at 4 months after randomization as measured by the Beck Depression Inventory.

**Blinding assessment.** To assess the quality of the subject blinding as to initial treatment assignment, we will ask each subject on Day 0 to speculate which treatment they received (actual or sham cryo). A Pearson's chi-square test will be used to compare the proportion of correct speculations in each treatment group.

For all analyses, alternative statistical methods will be used if the assumptions of the planned analyses are not met. For instance, t-tests or regression analyses on the change or percent change from baseline (depending on which is less correlated with baseline score) will be used instead of analysis of covariance when comparing groups on the 4-week outcomes if the treatment group-by-baseline interaction is significant. Transformations of the data or Mann-Whitney test or other non-parametric procedures will be used if the assumptions of normality and/or equal variances are not met.

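### Table 1 and the text disagree on when the Beck Depression Inventory is given, and only the text includes the Month 4 score that Aim 2c tests

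*Combined protocol and SAP*

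**What the plan says.** Three parts of the combined protocol and SAP bear on this.

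- **Section 9, Hypothesis 2c (text).** To limit burden, the schedule for the Beck Depression Inventory is restricted: "it will be administered only at the initial baseline and four months following each treatment intervention", for both the initial and the crossover treatment, with Month 12 added.
- **Section 9, Table 1.** Under the caption "Table 1. Summary of post-enrollment assessments", the Beck row carries three marks: Day 0 of the initial treatment, Day 0 of the crossover treatment, and Month 12. The footnote places the crossover in time: that "treatment intervention will occur between 4-6 months following the initial treatment".
- **Section 6 and the Statistical Plan.** Hypothesis 2c is that depression "will be significantly decreased 4 months following one cryoneurolysis procedure (as measured with the Beck Depression Inventory"). Aim 2c uses analysis of covariance, adjusted for the baseline score, to assess "the treatment effect of cryoneurolysis versus sham on depression at 4 months after randomization".

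The paragraph on Type I error places Aim 2c last in the gatekeeping order, after Aims 1, 2a and 2b. Nothing in the document reconciles the table with the text.

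**The concern.** Table 1 is the protocol's only grid of instruments by time point, and its Beck row leaves out the one time point at which depression is formally compared between groups. All questionnaires are given by telephone from one centre, so an error in the call schedule would affect subjects from all seven sites alike.

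A missed Month 4 Beck score could not be repaired later:

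- **Carrying forward.** The rule under Dropouts depends on a Month 3 assessment, and neither schedule has a Month 3 Beck score. The only earlier Beck score is the baseline, so carrying it forward would set the change to zero by construction.
- **Best and worst scores.** The fallback assigns the best score to sham and the worst to active treatment. It is meant for a few dropouts (about 7% are expected) and would say nothing useful if applied to a large share of subjects.
- **Month 12.** The plan itself says that the treatment effect cannot be directly assessed then, because of the crossover.
- **Crossover Day 0.** This score exists only for volunteers. The plan warns of selection bias in that group and expects more of them to come from the sham arm.

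**Working it through.** No sample size, power or significance level enters, so the check is a comparison of the two schedules.

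**Columns of Table 1.** There are 7 time points after the initial treatment (Days 0, 1, 7; Months 1, 2, 3, 4), the same 7 after crossover, and Month 12: 7 + 7 + 1 = 15. The Beck row has 15 cells, with marks in cells 1, 8 and 15. The six other rows are marked in all 15.

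| Time point | Text, Hypothesis 2c | Table 1, Beck row | Used by Aim 2c |
|---|---|---|---|
| Initial baseline / Day 0 | yes | yes (cell 1) | yes, covariate |
| Month 4 after initial treatment | yes | no (cell 7 empty) | yes, outcome |
| Crossover Day 0 | no | yes (cell 8) | no |
| Month 4 after crossover | yes | no (cell 14 empty) | no |
| Month 12 | yes | yes (cell 15) | no |

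The text gives 4 administrations and the table 3. They agree on 2 time points and differ on 3: both Month 4 scores are in the text only, and crossover Day 0 is in the table only. Because the text says the instrument is given only at the listed times, the crossover Day 0 mark conflicts with it and cannot be read as a harmless addition.

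**Consequence if the table is followed.**

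- Subjects who decline crossover have Beck scores at baseline and Month 12 and nothing between.
- Subjects who cross over have a score at crossover Day 0, which is 4 to 6 months after the initial treatment and so up to 6 − 4 = 2 months later than the Aim 2c time point.
- Month 12 falls 12 − 6 = 6 to 12 − 4 = 8 months after the crossover treatment, so it does not supply the missing Month 4 score after crossover either.

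**Consequence if the text is followed.** Every score that Aim 2c needs is collected. The loss is then zero, and the table is simply wrong.

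**The case against.** The case for treating this as no more than an editorial note has four parts.

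**The row may have been damaged in reading.** In the machine-read copy the month labels of Table 1 are visibly shifted: the label for Month 1 stands in the Day 7 column in both blocks. Full rows cannot reveal a misplaced mark, and the Beck row is the only sparse one. Its three marks also sit in the first cell of each header block, as might happen if marks had been merged by block. A sideways shift alone would not turn four marks into three, but a merged or dropped mark cannot be excluded. This stands, and it is why the first step is to look at the original page. On the other side, the three marks also make sense as an authored schedule: the start of each treatment period plus the final call.

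**The intent is plain.** Hypothesis 2c, the sentence on administration and Aim 2c all name 4 months. This also stands. A reader might infer from Table 1 that the design omits the Month 4 Beck assessment; the text rules that out.

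**Nothing says that the callers work from the table.** The caption calls it a summary, the callers are trained in the instruments, and every subject already has a Month 4 call for the primary endpoint. This stands too. A reader might infer that the Aim 2c outcome will go uncollected and the aim become unanalysable. The documents support that only on the condition that the table is printed as read here and is followed over the text.

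**The reach is small.** One secondary aim is affected, and it is the last to be tested. The Brief Pain Inventory row is complete.

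What the objection does not remove is the contradiction. The only grid of time points and the sentence that restricts the instrument to certain times cannot both be right, and the consequence of following the wrong one is irreversible.

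**Conclusion.** The point holds as a contradiction between table and text, not as a fault in the choice of design. The two Beck schedules differ at three time points, and Table 1 lacks the Month 4 score that Hypothesis 2c and Aim 2c require.

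The size depends on which schedule is put into practice. With the table, subjects who decline crossover have no Month 4 score, and those who cross over have a self-selected one timed anywhere from 4 to 6 months. With the text, nothing is lost. The documents do not say which of the two the callers use, nor how many subjects are expected to cross over, so no share of missing data can be given.

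The conclusion assumes that the original page shows the Beck row as it appears in the machine-read copy. If the original carries the Month 4 marks, the gap for Aim 2c disappears. The primary endpoint is unaffected in every case.

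**What to change.** 1. Check the Beck row of Table 1 against the original page.
2. If it reads as described, align Table 1 with the text under Hypothesis 2c: mark Month 4 after the initial treatment and Month 4 after crossover, and keep initial baseline and Month 12.
3. Decide on crossover Day 0. Remove the mark, or, if a score before the second treatment is intended, add that time point to the text.
4. Carry the agreed schedule into the call script and the data-collection forms.

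The cost is a corrected table and call script. The Month 4 calls already take place, and the protocol allows an additional 15 minutes for any call that includes the Beck Depression Inventory. Relative to the schedule in the text, restoring the Month 4 marks adds no burden.

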## Statistical Plan and Data Analysis

The randomized groups will be descriptively compared on baseline demographic and pain variables using descriptive statistics. In particular, groups will be considered well-balanced on a particular baseline variable if the standardized difference (difference in means or proportions divided by the pooled standard deviation) is less than  $\sqrt{2/n}$ , where  $n$  is the per-group sample size. The primary analysis will be modified intention-to-treat, in which all randomized subjects who received any of the study treatment will be included and retained in their respective treatment groups.

**Aim 1: Primary outcome.** We will assess the average causal effect of cryoneurolysis versus sham/placebo on phantom limb pain intensity (average pain over past 72 hours) at 4 months after the initial treatment using analysis of covariance to adjust for baseline pain intensity and any imbalanced baseline variables (see above). Results will be summarized as the least squares difference in means at 4 months and 95% confidence interval. Mean and standard deviation change from baseline intensity will also be summarized. Similar analyses will be conducted for the secondary outcomes of current/present, worst and least phantom pain, as well as average and worst residual limb pain.

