## 9. RESEARCH DESIGN AND METHODS

This will be a multicenter, randomized, triple-masked (investigators, subjects, statisticians), sham/placebo-controlled, parallel (with optional crossover), human-subjects clinical trial to determine if cryoanalgesia is an effective treatment for intractable post-amputation phantom limb pain. We have included a diverse group of recruitment sites that will provide a broad representative patients sample. Study participants will be recruited at 7 centers, including 2 U.S. military, 2 Veterans Affairs, and 3 civilian university medical centers (1 private, 2 public), within a wide geographic range including the South, Midwest, East and West Coasts, providing a study sample with ethnic, racial, geographic and socioeconomic diversity.

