Randomization will be stratified by enrolling institution in randomly chosen block sizes. Randomization lists will be created using computer-generated tables by the Cleveland Clinic. Treatment group assignment will be conveyed to the enrolling sites via the same secure web-based system (RedCap) used to collect and collate all post-intervention endpoints (see "Data Collection" paragraph below). The first digit of the randomization numbers will be a letter denoting the enrolling center (of 7 possible); and, the next two digits will be integers beginning from 1 and increasing for each center. Cryoneurolysis probes are available that either (1) pass nitrous oxide to the tip inducing freezing temperatures; or, (2) vent the nitrous oxide at the base of the probe so that no gas reaches the probe tip, resulting in no temperature change (PainBlocker, Epimed, Farmers Branch, Texas). Importantly, these probes are indistinguishable in appearance, and therefore treating physicians, subjects, and all clinical staff will be masked to treatment group assignment [only one individual at each institution will be unmasked and will provide the treating physician/investigator with the correct probe after opening the randomization envelope]. Unmasking will not occur until statistical analysis is complete (termed "triple masked").

**Intervention.** The potential cryoneurolysis sites will be again cleansed with chlorhexidine gluconate and isopropyl alcohol. With the same ultrasound transducer used to previously administer local anesthetic, the target nerve will again be identified in a transverse cross-sectional (short axis) view at or distal to the deposition of local anesthetic. A cryoneurolysis device (PainBlocker, Epimed, Farmers Branch, Texas) will be used with the appropriate randomization-designated probe (either active or sham/placebo) and nitrous oxide (**Figured in the Background section**). An angiocatheter will be inserted through a local anesthetic skin wheal in-plane beneath the ultrasound transducer and directed until the probe tip is immediately adjacent to the target nerve (lidocaine 2% will be administered, as needed, to anesthetize the angiocatheter track). The angiocatheter needle will be

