**Outcome measurements (endpoints).** We have selected outcome measures that have established reliability and validity, with minimal inter-rater discordance, and are recommended for chronic pain clinical trials by the Initiative on Methods, Measurement, and Pain Assessment in Clinical Trials (IMMPACT) consensus statement. ***The primary end point will be the difference in average daily phantom pain intensity at baseline and 4 months following the initial intervention (measured with the NRS as part of the Brief Pain Inventory).*** The primary analyses will compare the two treatments (inter-subject comparisons) during the initial treatment period in which half of the subjects will receive active cryoneurolysis and the other half a sham/placebo treatment. Endpoints will be evaluated at baseline and post-treatment (Day 0), Days 1 and 7; and Months 1, 2, 3, 4, and 12,

(Table 1). These same time points through Month 4 will be evaluated following the optional second (crossover) treatment.

The questionnaire will differentiate among multiple dimensions of limb pain:

**Residual limb (“stump”) pain:** painful sensations localized to the portion of limb still present.

**Phantom limb sensations:** non-painful sensations referred to the lost body part.

**Phantom limb pain:** painful sensations referred to the lost body part.

Each type of pain/sensation will be defined for subjects immediately prior to questionnaire application at each time point, and subjects will be instructed to specifically address phantom limb pain when responding to the various questions. In addition, since there is a strong correlation between phantom and residual limb pain, we will specifically inquire about both types of pain. Each time the questionnaire is applied, subjects will be instructed to respond for the previous 3 days (e.g., worst pain during the previous 3 days) because studies have suggested that patients have “increasing difficulty actually remembering symptom levels beyond the past several days.” Exceptions will be on Day 1 for both the initial and crossover treatments because at these time points, the interest is in subjects’ experiences subsequent to the treatment and not prior to the intervention. During these two days, subjects will be instructed to respond for the period of time since their treatment.

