## 10. HUMAN SUBJECTS

Approximately 60 subjects will be enrolled at UC San Diego, of approximately 200 participants at all sites.

**Inclusion criteria:** Adult patients of at least 18 years of age, (1) with a lower limb traumatic or surgical amputation at least 12 weeks prior to enrollment distal to the hip (femoral head remaining); (2) who experience at least moderate phantom limb pain—defined as a 3 or higher on the Numeric Rating Scale (NRS; 0-10, 0= no pain; 10=worst imaginable pain)—at least daily for the previous 2 months. (3) accepting of a cryoneurolysis procedure; and, (4) willing to avoid both changes to their analgesic regimen as well as elective surgical procedures from 1 month prior to and at least 4 months following the initial cryoneurolysis procedure.

**Exclusion criteria:** (1) allergy to amide local anesthetics; (2) pregnancy; (3) incarceration; (4) inability to communicate with the investigators; (5) morbid obesity (body mass index > 40 kg/m^2); and, (6) possessing any contraindication specific to cryoneurolysis such as a localized infection at the treatment site, cryoglobulinemia, cold urticaria and Reynaud's Syndrome.

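### Enrolling institution, the stratification factor, is in no analysis model, and the Aim 2b model lists no baseline interference scores: a minor loss of precision that SAP wording can recover

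*Combined protocol and SAP*

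**What the plan says.** - **Randomisation** (Section 9, treatment group assignment): "Randomization will be stratified by enrolling institution in randomly chosen block sizes". Section 9 opens with "Study participants will be recruited at 7 centers, including 2 U.S. military, 2 Veterans Affairs, and 3 civilian university medical centers". Section 10 adds that "Approximately 60 subjects will be enrolled at UC San Diego, of approximately 200 participants at all sites".
- **Aim 1** (Statistical Plan and Data Analysis): the groups are compared "using analysis of covariance to adjust for baseline pain intensity and any imbalanced baseline variables (see above"). A variable counts as imbalanced when its standardised difference reaches sqrt(2/n), with n per group. The candidates are described only as demographic and pain variables.
- **Aim 2a** (Secondary outcomes): a Mann-Whitney test, with proportional odds regression for imbalanced variables where appropriate.
- **Aim 2b**: a "mixed effects multivariate model (random subject term, fixed treatment effect, unstructured correlation matrix"), used first to test whether the effect differs across the seven interference measures. If it does, each measure is analysed on its own.
- **Aim 2c**: "Analysis of covariance adjusting for baseline score will be used to assess the treatment effect".
- **Data available** (Outcome measurements): "Endpoints will be evaluated at baseline and post-treatment (Day 0), Days 1 and 7". Table 1 includes the Brief Pain Inventory on Day 0.
- **Testing order** (Type I error): Aim 1, 2a, 2b, then 2c. A set is tested only if at least one outcome in the set before it is significant.

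**The concern.** A factor used to stratify randomisation normally goes into the analysis. Stratified blocks balance the arms within each centre, so the true variance of the treatment contrast excludes between-centre differences. A model without centre leaves those differences in its residual variance, and the standard error comes out too large. The imbalance screen does not fill this gap. Institution is neither a demographic nor a pain variable, and stratification keeps it balanced, so the screen would seldom bring it in by the final analysis.

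Aim 2b raises a separate question. The plan adjusts for baseline where it analyses pain intensity and depression, but the terms given for the interference model include no baseline score. At stake is precision in a secondary aim that also controls access to Aim 2c.

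**Working it through.** **Reproducing the plan's sample size.** Inputs (Sample size considerations): difference 1.7, SD 3.0, correlation 0.50, two-sided 0.05, power 0.90, four looks.
- SD of change = 3.0 × sqrt(2 × (1 − 0.5)) = 3.0, which gives 66 per group for a fixed design.
- With the Table 2 boundaries, the four-look design needs 71.8 per group; power at 72 is 0.901. The stated 72 per group (N=144) reproduces.
- ANCOVA has residual SD 3.0 × sqrt(1 − 0.5²) = 2.60 (variance 6.75) and power of about 0.96 at 72 per group. There is room for a few prespecified terms.

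**Institution in the primary model.** The share s of residual variance lying between sites is assumed. Site sizes are either 30% at one centre (60/200) with 11.7% at each of the other six, or seven equal sites.
- With site fractions p, omitting site multiplies the SE by about sqrt(1 + q·s/(1 − s)), where q = 1 − Σp². Here q is 0.828 for the 30% split and 0.857 for equal sites.
- At s = 5%: sqrt(1 + 0.828 × 0.05/0.95) = 1.022. At s = 10%: sqrt(1 + 0.828 × 0.10/0.90) = 1.045. The cost of estimating site, about 0.1%, comes off these.
- Simulation of the four-look design agrees (6000 trials per setting; assumed blocks of 2, 4 and 6). These runs pooled sites with fewer than 8 subjects, which has little effect at N=144:

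| Assumed site share | SE without / with site at N=144 (30% split; equal sites) |
|---|---|
| 0% | 0.999; 0.999 |
| 2% | 1.007; 1.008 |
| 5% | 1.020; 1.021 |
| 10% | 1.044; 1.046 |

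- At a 10% share, null rejection is 3.7-3.8% without site and 4.4-4.6% with it. The design's own rate with both boundaries binding is 4.6%.
- Over shares of 0-10%, adding site changes overall power by −0.1 to +0.4 points.
- If sites do not differ, seven unpooled site terms raise the first-look SE (N=36) by 2.3-2.7%.

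**Baseline scores in Aim 2b.** The plan gives a baseline correlation for the NRS only (0.50), so r for the interference items is assumed.
- Adjustment multiplies error variance by 1 − r²: 0.91, 0.75 and 0.51 at r = 0.3, 0.5 and 0.7. The reductions are 9%, 25% and 49%.
- This takes cross-item correlations over time to be proportional to those within an item. If they are 20% lower or higher at r = 0.5, the factor is 0.83 or 0.67.
- Illustration with assumed between-item correlation 0.6 and level 0.05: the mean of seven items has variance (1 + 6 × 0.6)/7 = 0.657 in SD² units. SE = sqrt(2 × 0.657/n) unadjusted, times sqrt(0.75) adjusted at r = 0.5. Power = Φ(d/SE − 1.96):

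| Per group | SE unadjusted / adjusted | Power at d = 0.3 / 0.4 / 0.5, unadjusted | Adjusted |
|---|---|---|---|
| 72 | 0.135 / 0.117 | 60% / 84% / 96% | 73% / 93% / 99% |
| 50 | 0.162 / 0.140 | 46% / 69% / 87% | 57% / 81% / 95% |

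The second row is the plan's expected total of 100 under the alternative. The effect sizes d, in SD units, are assumed.

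**The case against.** The strongest reply is that little is at risk. All follow-up questionnaires "will be administered by telephone from the University of California San Diego by research coordinators specifically trained", so differences in how sites collect the outcome should be small. At site shares of 0-2% the omission costs under 1% in SE. That stands. The mix of military, Veterans Affairs and civilian populations argues for some difference, but its size is unknown.

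The Aim 2b parenthesis may also not be a full specification. It omits the measure effect and the interaction that the next words rely on, so its silence on baseline may be a gap in wording rather than a decision. That is fair. It is still a reason to write the term in, since Aims 1 and 2c name theirs.

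Three stronger readings are tempting, and the documents do not support them:
- A reader might infer that omitting a stratification factor biases the result or inflates type I error. The error runs the other way: the SE is too large, and only if sites differ.
- A reader might infer that the primary comparison is underpowered. Planning used the change-score SD, so ANCOVA power is about 0.96 on the plan's own inputs.
- A reader might see the imbalance screen as a route to choosing covariates by result. Its threshold is one standard error, so it flags 31.7% of perfectly randomised variables, and its candidate list is open. But the rule is numeric and uses baseline data only, and simulated null rejection stayed at 2.5-4.9%. Whether to keep it in the primary model is a trade-off: moving flagged covariates out loses 1.0-1.6 points of power if they explain 30% of residual variance (assumed; 14 or 9 candidates).

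**Conclusion.** The point holds as a minor one. The text is clear that institution stratifies the randomisation and appears in no model, and that the Aim 2b terms include no baseline score. The primary test is slightly conservative only if sites differ, by about 2% in SE at a 5% share and 4-5% at 10%; its validity is not in question. Aim 2b has more to gain, with 25% of error variance if the interference items behave like the NRS. The site shares, interference correlations, between-item correlation and effect sizes are all assumptions. The case for acting is that the data are already collected and the change is nearly free, not that the plan fails without it.

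**What to change.** - **Aim 1 and Aim 2c:** add enrolling institution to each ANCOVA, at every look for Aim 1.
- **Aim 2a:** replace the plain Mann-Whitney test with one stratified by institution (van Elteren), and include institution in any proportional odds model. Changing only the regression would leave the named test unstratified.
- **Aim 2b:** add each measure's baseline score, with its own coefficient by measure, and institution. Carry the same covariates into the single-measure analyses used if the interaction is present.
- **Small centres:** if centres must be combined, fix the grouping in advance by centre type (military, Veterans Affairs, civilian) and keep it at every look. Pooling on observed counts would change the model as data accrue: a rule of fewer than 8 per site leaves about two strata at N=36 and about seven at N=144.

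**Cost:** SAP wording and up to six degrees of freedom. If sites do not differ, the SE rises by about 0.1% at N=144 and by 2-3% at the first look with seven separate sites. Grouping by type uses two degrees of freedom but leaves differences between centres of the same type in the residual. Sample size, visits and procedures do not change.
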